First, we will obtain n-best list speech recognition of the COPE interaction (46). This will help mitigate recognition errors in the next stage. Until recently, audio recording transcription was fraught with challenges particularly in sessions involving two or more speakers. Advances in audio signaling and speech recognition have brought technology for automating language analysis within reach. Recent research has suggested that text-based features may be more effective than using audio features alone when classifying fidelity in behavioral research (47). Automatic speech recognition software will be used to transcribe sessions, and the resulting words will be used in a text-based model of fidelity. Once transcripts are obtained, two approaches will be developed and contrasted: (1) comparison with a reference delivery and (2) a supervised classification approach. The first has the advantage of needing only a small number of excellent deliveries and several acceptable deliveries, for each of the seven dimensions, while the other needs a larger set of labeled data but would potentially lead to a higher accuracy of prediction.

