### Comparison or similarity to reference (Steps A and B):

Our approach will leverage techniques widely used in the evaluation of automatically produced content, such as machine translation and automatic text summarization. In these applications, it is not feasible to track system improvement with human judgements of quality. Instead, most of the progress is measured by computing similarity between a set of sample reference text (i.e. what a “good” translation or a good summary would be) and the system output. Such automatic evaluation approaches are widely used for machine translation (48) and summarization (49). While there have been some concerns that the automatic measures are not fine enough to distinguish between levels of very good context, these measures show strong ability to distinguish “very bad” content (50, 51) (or poor fidelity) aligns with the needs of our project.

FIGURE 5: Development and validation of Fidelity Monitoring Program

**PHASE 2 - Evaluation of Online Training Program in Interventionist Uptake and Fidelity:** Phase 2 of this study involves a series of activities designed to evaluate the whether an online training program is the same or better in improving interventionist uptake of- and fidelity to-COPE principles and protocols compared to a high intensity face-to-face traditional form of training.

**Eligibility and enrollment:** Ten participating Trinity PACE Organizations will participate via webinar in a brief orientation/training to the study and project logistics. Next, Trinity Health PACE organizations will be randomized into two groups using the re-randomization procedures described in the paragraph below; 5 PACE organizations will serve as the “control” site in which training will be provided via the traditional high intensity face-to-face.; 5 PACE organizations will serve as the comparison and be trained through the online training site. Prior to randomization, we will carefully examine PACE organizations on important variables such as size, location (urban; rural) percent of persons with dementia, and staff: participant ratio. In each site, one occupational therapist (OT) and one nurse (RN) will be trained (e.g., 5 OTs and 5 RNs in traditional sites; 5 OTs and 5 RNs in online training sites for a total of 10 OTs and 10 RNs or 20 healthproviders).

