**Analysis of Aim 1:** To compare the training programs on Interventionist uptake. We will conduct pre and post surveys to assess changes in knowledge and assess satisfaction with the training. COPE interventionists will need to demonstrate Knowledge and Competency in treatment delivery to be certified by PIs and [name] in COPE delivery, a measurement approach we use effectively in our trials (56). We will conduct a noninferiority analysis to determine if online training compared to high intensity face-to-face training results in same or better in Knowledge and Competency scores. Independent-samples t test, 2 test, and Fisher's exact test will be used to compare the groups.

**Analysis of Aim 2:** The fidelity model will be used to compare sessions delivered by interventionists under the two different conditions (online versus traditional face-to-face training conditions). The accuracy of the computationally derived "best model" automatic summarization fidelity ratings ("excellent", "acceptable", "problematic") will be evaluated against human ratings for all recorded sessions (N=600). The comparison of the automated fidelity relative to human fidelity rating will be evaluated through a comparison of agreement (Kappa coefficient). Human ratings will

be conducted by Ors [name] and [name] using the COPE Adherence Scale (1= excellent, .5 = acceptable, 0=problematic).

**PHASE 3 - Efficacy of COPE on PACE participant outcomes by type of COPE training:** This aim will be accomplished by evaluating dyad outcomes of the COPE program under the two different training approaches. Following training, each of the PACE organizations will enroll 5 persons with dementia and their caregivers in the study. This will yield 50 family dyads (25 dyads in traditional training sites and 25 dyads in online training sites). At 4 months, all dyad study outcomes will be assessed (Table 2).

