**PHASE 1b** -The Fidelity Monitoring Program: We seek to develop a scalable approach to assess fidelity to the COPE Program when it is implemented in a real-world setting such as PACE using computational linguistics techniques (e.g. natural language processing). The essence of fidelity to the Core Principles of COPE program will be captured via the examples provided in Table 1 (see C.4 above) by using automatic classification programs that evaluate both the content that should be included in COPE sessions and the style of delivery. While automatic classification programs have been applied to measure quality metrics of transcribed narratives in the field of psychotherapy (21), it has not been used to measure other aspects of quality- namely fidelity to evidence-based practices or dementia care and caregiver support programs. The development of the automated Fidelity Monitoring Program will occur in three steps (Figure 5) and will be carried out by a technical team consisting of an expert in content analysis, [name], and a consultant expert in speech recognition and prosody, [name]. Co-I- I [name] has worked extensively on automatic summarization, evaluation of automatic summarization, and readability and linguistic style. The ultimate goal of our efforts is to develop a system that- given a recording of a COPE delivery session (e.g. in real-time immediately after interaction between the clinician and the caregiver)- produces a three-tiered score, indicating if the fidelity was excellent, acceptable, or problematic. Special emphasis will be given to the accuracy of identifying problematic COPE fidelity which is not fateful to training and may not produce the same desired outcomes as intervention delivered with higher fidelity. Before recruitment begins and COPE sessions can be recorded, secondary analysis will be performed on audio recordings obtained for fidelity monitoring from the TAP study. As a precursor to the COPE program, the TAP audio recordings will be examined for fidelity linguistic purposes. Exploratory analysis will also be performed on audio recordings of baseline interviews of consenting research participants. After obtaining caregiver consent, baseline interviews and COPE interventionist sessions will be recorded and automatically transcribed via a HIPAA-compliant, Penn-approved third party. Transcriptions will be kept on a secure password-protected Penn Nursing laptop and PHI will be removed. The resulting anonymous transcripts will be saved on a secure password-protected server and original transcripts that include PHI will be destroyed immediately.

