### **Analysis Plan**

Analysis of Aim 1: To compare the training programs on Interventionist uptake. We will conduct pre and

post surveys to assess changes in knowledge and assess satisfaction with the training. COPE interventionists will need to demonstrate Knowledge and Competency in treatment delivery to be certified by Pis and [name] in COPE delivery, a measurement approach we use effectively in our trials (56). We will conduct a noninferiority analysis to determine if online training compared to virtual/remote training results in same or better in Knowledge and Competency scores. Independent-samples t-test, 2 test, and Fishers exact test will be used to compare the groups.

**Analysis of Aim 2:** The fidelity model will be used to compare sessions delivered by interventionists under the two different conditions (online versus virtual/remote training conditions). The accuracy of the computationally derived best model automatic summarization fidelity ratings (excellent, acceptable, problematic) will be evaluated against human ratings for all recorded session (N=600). The comparison of the automated fidelity relative to human fidelity rating will be evaluated through a comparison of agreement (Kappa coefficient). Human ratings will be conducted by Drs [name] and [name] using the COPE Adherence Scale (1= excellent, .5 = acceptable, 0=problematic).

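### The accuracy analysis for the automated fidelity rating names only an overall kappa of unspecified type, with no measure for the problematic sessions that the tool is meant to catch

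*Combined protocol and SAP*

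**What the plan says.** The tool "produces a three-tiered score, indicating if the fidelity was excellent, acceptable, or problematic" (Study Procedures, Phase 1b). Human raters score the same three levels on the "COPE Adherence Scale (1= excellent, .5 = acceptable, 0=problematic"), so the scale is ordered and equally spaced.

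The tool's priority is explicit: "Special emphasis will be given to the accuracy of identifying problematic COPE fidelity" (Study Procedures, Phase 1b; the Research Plan has a matching sentence).

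In the Analysis Plan, under Analysis of Aim 2, the ratings of the best model are "evaluated against human ratings for all recorded session (N=600"), and the automated rating relative to the human one is to be "evaluated through a comparison of agreement (Kappa coefficient"). The Aim 2 paragraph in the Research Plan says the same: the comparison "will be evaluated through a comparison of agreement (Kappa coefficient"). Neither place states weights, a target value, a confidence interval or a measure for one class.

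On development, the Research Plan says that "two approaches will be developed and contrasted: (1) comparison with a reference delivery and (2) a supervised classification approach". It gives no rule for deciding which becomes the best model.

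**The concern.** The emphasis on problematic sessions never reaches the analysis. Kappa summarises agreement over all three levels. When problematic sessions are a minority, most of the table is excellent and acceptable sessions, and a tool can score well on those alone. A respectable kappa would then say little about the task the tool was built for.

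The result also matters beyond validation, because the fidelity model is used to compare sessions between the two training arms. If sensitivity and specificity are the same in both arms, a true difference in the proportion of problematic sessions is multiplied by (sensitivity + specificity - 1). With specificity 1, a tool with sensitivity 0.45 keeps 45% of the difference, and one with sensitivity 0.95 keeps 95%. In a same-or-better comparison, shrinking a real deficit favours the new training.

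**Working it through.** **The plan's N.** There are 50 dyads (Phase 3), each with up to 10 OT sessions and up to two RN visits (Study duration). 50 x (10 + 2) = 600, which matches. OT sessions alone give 50 x 10 = 500; adding the RN telephone session gives 50 x 13 = 650. Since the counts are maxima, 600 is a ceiling.

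**Assumed inputs.** The documents give no prevalence of problematic sessions and no error rates, so these are assumptions.
- Human mix at 15% prevalence: 50/35/15% excellent/acceptable/problematic, or 300/210/90 sessions. At other prevalences the remainder keeps the 50:35 split.
- Tool A: sensitivity 0.95 for problematic, misses called acceptable, 25% swaps between excellent and acceptable.
- Tool B: sensitivity 0.45, misses split equally between excellent and acceptable, 93% correct on excellent and 92% on acceptable.
- Neither tool calls a session problematic falsely (specificity 1).

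**Expected counts at 15%** (rows human, columns tool, in the order excellent, acceptable, problematic; fractions arise because these are expectations).
- A: 225, 75, 0 / 52.5, 157.5, 0 / 0, 4.5, 85.5. Column totals 277.5, 237, 85.5.
- B: 279, 21, 0 / 16.8, 193.2, 0 / 24.75, 24.75, 40.5. Column totals 320.55, 238.95, 40.5.

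**Unweighted kappa** = (po - pe)/(1 - pe).
- A: po = 468/600 = 0.780; pe = (300 x 277.5 + 210 x 237 + 90 x 85.5)/360,000 = 0.391; kappa = 0.389/0.609 = 0.64.
- B: po = 512.7/600 = 0.8545; pe = (300 x 320.55 + 210 x 238.95 + 90 x 40.5)/360,000 = 0.417; kappa = 0.438/0.583 = 0.75.

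**Range over prevalence**, same error rates:

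| Problematic | Kappa A (sens. 0.95) | Kappa B (sens. 0.45) | Ranked first |
|---|---|---|---|
| 5% | 0.55 | 0.81 | B |
| 10% | 0.60 | 0.78 | B |
| 15% | 0.64 | 0.75 | B |
| 20% | 0.67 | 0.72 | B |
| 30% | 0.71 | 0.67 | A |

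At 15% prevalence with A's swap rate cut to 15%, po = 0.865, pe = 0.393 and kappa = 0.78, so A leads B's 0.75.

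**Quadratic-weighted kappa** = 1 - (observed weighted disagreement)/(expected weighted disagreement), with weight 0.25 for adjacent levels and 1 for excellent against problematic. At 15% prevalence:
- A: observed 0.25 x (75 + 52.5 + 4.5)/600 = 0.0550; expected 0.2578; kappa = 0.79.
- B, misses split: 0.71, so the order is right.
- B, all misses called acceptable: observed 0.25 x (21 + 16.8 + 49.5)/600 = 0.0364; expected 0.2282; kappa = 0.84. The tool that misses 55% of problematic sessions leads again.

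**A second pair**, with excellent:acceptable 2:1. One tool has sensitivity 0.20 and is 95% correct elsewhere; the other has sensitivity 0.90, specificity 98% and is 80% correct elsewhere. Unweighted kappa for the poor against the good detector, the range covering where the misses fall:
- 5% prevalence: 0.815-0.820 against 0.628 (wrong order).
- 10%: 0.752-0.763 against 0.663 (wrong order).
- 20%: 0.639-0.665 against 0.711 (right order).
- 30%: 0.542-0.581 against 0.740 (right order).

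At 10%, quadratic kappa also misranks if the misses are called acceptable (0.831 against 0.791), but not if they are called excellent (0.507 against 0.791).

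**The case against.** The strongest reply is that nothing in the plan is wrong as written. Kappa requires the full three-by-three table, so sensitivity and specificity can be read from it later, and the misranking comes from inputs we chose. Both statements are true. The ordering does reverse at higher prevalence or with a more exact tool A. But a measure that can be recovered is not one that has been pre-specified, and the protocol itself singles out this class.

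A reader might infer several stronger points that the documents do not support.
- *That the plan uses unweighted kappa.* It says only kappa coefficient, and the 1/.5/0 scoring is compatible with weights. Weighting is not a complete answer either, as shown above.
- *That kappa selects the model.* The Aim 2 text applies kappa to a model already called best. No selection rule is stated.
- *That the sponsor expects the tool to blur the upper levels.* The remark that "the automatic measures are not fine enough to distinguish between levels of very good context" reports concerns about measures used in translation and summarization. It stands under the similarity-to-reference approach only.

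Finally, Figure 5, on development and validation, is not shown and some pages were removed. That kappa is the only measure can be said of the available text alone.

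**Conclusion.** The point holds as a mismatch between a stated priority and the stated analysis. The protocol emphasises problematic sessions, and the visible analysis contains no measure specific to them. An overall kappa does not fill that gap. In the first pair above, unweighted kappa puts a 45%-sensitivity tool ahead of a 95% one by 0.26 at 5% prevalence (0.81 - 0.55), narrowing to 0.05 at 20% (0.72 - 0.67); by 30% the order is right.

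This shows that misranking is possible, not that it will happen. It needs problematic sessions to be uncommon and the better detector to be less exact between the upper two levels. The first is plausible, since interventionists must be certified before delivering COPE, but the documents give no figure. The correction is worth making because it costs little and follows from the protocol's own aim.

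**What to change.** In Analysis of Aim 2, in both places where it appears:
1. Make sensitivity and specificity for problematic versus not problematic, against the human rating, the main accuracy measure. Use the pair when the reference-comparison and supervised approaches are contrasted, and state beforehand how the two values are weighed together.
2. Report quadratic-weighted kappa, named as such, as the secondary measure of overall ordinal agreement.
3. Give 95% confidence intervals that allow for clustering by interventionist, and note that about 20 clusters (10 OTs and 10 RNs) is few for such methods.

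The cost is a few lines of analysis text and code. The recordings, raters and three-by-three table are unchanged. The downside is imprecision if problematic sessions are few. At 5% prevalence there are 600 x 0.05 = 30 of them, and a sensitivity of 0.45 has half-width 1.96 x sqrt(0.45 x 0.55/30) = 0.18 before any allowance for clustering. At 15% (90 sessions) it is 0.10. That uncertainty should be reported; an overall kappa would not show it.
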